	
Exclusion:
 
Any vulval skin dermatoses excluding medical management of vaginismus
 
Transgender male / on testosterone therapy
 
Symptoms of genital herpes episode in preceding 3 months
 
Unable to speak/ understand English or needing an interpreter
 
Declines to be enrolled in research study
 
Pregnancy

Statistical methodology and analysis (if applicable)	n/a
Study duration	Up to 48 months

5. Introduction

VITA DIVA- Vibration Therapy And Dilators for Vaginismus

Vaginismus results from the involuntary spasm of the pelvic floor muscles which surround the vaginal wall. This can make sexual intercourse uncomfortable, painful, or impossible, with resultant impacts on a woman's sexual pleasure and ability to conceive. There is often overlap with vulvodynia (also termed vestibulodynia), chronic vulvar pain of at least three months duration. Various clinical definitions have been proposed for vulvodynia or vestibulitis.

Successful treatment for both vulvodynia and vaginismus relies often on both medical and psychosocial interventions alongside self-help and practice. Current medical therapy for vaginismus often consists of the use of topical local anaesthetic gel, sometimes in addition to oral medications such as low dose Tricyclic Antidepressants together with recommendation of progressive vaginal dilator therapy (often termed systemic desensitisation) and physiotherapy. The fact there is not a clearly culpable etiology (and indeed causes are likely to be multifactorial) means that there is no 'gold standard' treatment for vaginismus and vulvodynia (Zolnoun, 2008). A multi-modal approach is recommended.

Anecdotally, some women find that clitoral stimulation can sometimes have a positive impact on the ability to progress with vaginal dilator treatment and general enjoyment of sexual intimacy, but this has not yet been evaluated in a research setting.

Background

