This proposed study looks at the feasibility and acceptability of using clitoral vibration therapy, alongside current therapy, for women with vaginismus. It is likely that many, if not most, of these women will also have an element of vulvodynia. We propose that the use of external clitoral or vulval vibration therapy is likely to be acceptable in most women with vaginismus, based on acceptability of vulvar vibration therapy in women with vulvodynia. We propose based on the evidence above that vibrator therapy may help women with female sexual dysfunction to use vaginal dilators, based on study showing improvements with sexual distress and satisfaction.

Enrollment

This is a nonrandomized controlled trial, with the initial cluster of patients receiving standard therapy, and the second cluster receiving standard therapy plus vibrator. We aim to recruit an initial 15 participants who will receive standard therapy, and another 15 who will receive an external vibrator.

We expect this to take place over approximately 24-48 months. Enrollment of patients will be from a joint psychosexual clinic led by a medical doctor and a clinical psychologist. Female patients are referred to this clinic by General Practitioners, from within the Sexual Health service, or via Gynaecologists, frequently with complaint of difficulty or pain with penetrative sex. Inclusion and exclusion criteria have already been outlined.

Trial information will be given at the initial appointment. If the patient wishes to enrol, then an initial baseline questionnaire will be given, and a follow up questionnaire will be filled out by phone contact at 6-24 months afterward the initial consultation at the patients consent.

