5.4 Risks / benefits

Of 49 eligible patients with vulvodynia, 83% of those surveyed who had used vulvar vibration therapy for at least two weeks had found it an acceptable treatment (Zolnoun, 2008)

Rubin et al published a clinical reference guide on sexual devices for clinicians in 2019 which stated that risks associated with sexual devices (such as vibrators) were traumatic injury or infection. Since we are recommending use of the vibrator for external use only, barrier use over sexual devices if shared, and proper disinfection to reduce risk of infection (Rubin, 2019).

The treatment period duration is 6-12 months. other studies looking at vulvar vibration therapy as an intervention have study periods of approximately 3-6 months.. We find that this allows patients to have completed any recommended intervention.

6. Study objectives

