6.4 Secondary endpoint

Baseline and follow up questionnaires will be used specific to study and also FSDS and FISI.

7. Study population

Potential participants will be identified from the patients presenting to the Female Sexual Wellbeing Clinic. Identification of participants beyond this will not be needed. The identification of suitable participants will be done by the clinicians, using the inclusion and exclusion criteria taken into account. The clinic is a joint clinic run by a clinical psychologist and medical doctor, who will be providing the initial

questionnaire and the follow up phone interview. Medical students (with honorary contract obtained) may also carry out interviews but not consent for the study.

Potential participants will be advised of the study verbally and given a written leaflet during their clinic appointment. Enrolment will be offered on the day on the understanding that the patient can decide to leave the study at any point.

Informed consent will be obtained. Consent will be taken by either the medical doctor or clinical psychologist in clinic. Verbal explanation of the study, together with a leaflet explaining the study will be provided.

If the study participants wish to enrol on the day, they will be able to. This may be preferable for convenience to avoid having to return to the clinic. Otherwise they will have 24hrs - 1 week to enrol. Enrolling on the day may be a preferred option for the patient so they do not have to return to clinic again. If they wish, they can take the written information away with them and return on another day.

Participants will enrol for approximately 6-24 months; this will be from the initial consultation until the follow up questionnaire, although no contact in the interim will be required as part of the research project there may be contact as part of any medical or psychological intervention separate to the project.

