7.2 Exclusion criteria

- Unwilling or unable to give consent
- Transgender male / on testosterone therapy
- Inability to understand written and / or verbal English
- Current dermatological skin conditions requiring active treatment
- Genital herpes simplex virus symptoms within preceding 3 months
- Not reporting symptoms of vaginismus, and no evidence of vaginismus on clinical examination.

Pregnancy – via history from patient.

8. Study design

This study is a feasibility and acceptability study. The collection of qualitative data collection will be questionnaires, and interviews as described below. The data obtained will be analysed using thematic analysis to identify topics and patterns. In addition two formal, validated questionnaires will be used that can be scored to assess any change in sexual function and/or sexual distress.

Group 1 (Standard treatment)

We aim to recruit an initial 10-15 participants who will receive standard therapy with vaginal dilators and current medical management which usually consists of some or all of lidocaine gel (topical local anaesthetic applied to the vulva), tricyclic antidepressants (used in co-existing vulvodynia or vulval pain syndromes) and physiotherapy. Standard treatment also includes Group or individual psychotherapy.

Group 2 (Intervention)

In addition the standard treatment outlined above, the next 10-15 recruited will receive dilators and an external vibrator. This will take place over 6-24 months in a joint psychosexual clinic which is led by a medical doctor and a clinical psychologist.

Both groups:

Trial information will be given at the initial appointment. If the patient wishes to enrol, than an initial baseline questionnaire will be given for a patient to fill out after the clinic. A private space will be provided for the patient to do this, and there will be an offer for the patient to return to do this if preferred. Two formal, validated questionnaires will be carried out at baseline and follow up. These are the Female Sexual Distress Scale - R (FSDS) and the Female Sexual Function Index.

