The follow up questionnaires will be filled out by phone contact 6-24 months after the initial consultation at the patients consent if they agree to remain enrolled in the trial for both group 1 and group 2. This will take approximately 30 mins and will be arranged at a time convenient for the patient. This interview will be carried out by a doctor. Answers will be recorded directly onto the follow up questionnaire proforma.

4 point Likert scale 1 (Strongly disagree) to 4 (Strongly agree)

9. Study procedures

- Informed consent – verbal and written will be given, patients will be offered opportunity to enrol on the day (for convenience) or to return at another point to enrol.
- Screening and recruitment – as outlined previously recruitment will be directly from clinic
- Randomization – this is a non-randomized controlled trial, as trial participants need to be identified as time goes on, and a certain number of control and intervention participants are needed. The initial 10-15 recruited will receive standard treatment, and then the next 15 will receive intervention.

Study interventions

Study intervention	Contact (Visit) 1	Contact 2		
Medical history	X			
Consent	X			
Baseline Questionnaires (FSDS, FSFI, custom questionnaire)	X			
Phone Interview (FSDS, FSFI, custom questionnaire)		X		

Vaginal dilators will be provided to both groups (if available) and external genital vibrators to the second (intervention) group.

- Concomitant medications – per standard treatment, patients with vulvodynia may be prescribed topical lidocaine gel and may also receive nortriptyline if there is unprovoked vulvodynia present.
- Criteria for discontinuation – if patients withdraw consent for being enrolled in the study then follow up will discontinue.
- Procedure for collecting data, including Case Report Forms (CRFs) and storage: CRFs will be filled out electronically, and stored in a password protected file. The research data will be archived for 25 years according to Queen Mary University of London/ Barts Health NHS Trust policy, JRMP SOP 20.

- Follow up will be via phone interview. Patients enrolled will receive a contact email address in case of queries in the meantime during research period.
- End of study duration will be at follow up questionnaire (at 6-24 months post initial appointment and questionnaire)

10. Assessment and management of risk

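### The single follow-up call may fall anywhere from 6 to 24 months with no target time, while the vibrator group is always enrolled second, so follow-up time can differ by group; the stated durations also need reconciling.

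*Protocol*

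**What the plan says.** - **Follow-up.** Section 8 (Both groups): "The follow up questionnaires will be filled out by phone contact 6-24 months after the initial consultation". The call is arranged to suit the patient, and the window applies to both groups. Section 9 lists one contact after baseline. Section 7 says "Participants will enrol for approximately 6-24 months; this will be from the initial consultation until the follow up questionnaire", with no research contact required in between.
- **Order of enrolment.** Section 9: "The initial 10-15 recruited will receive standard treatment, and then the next 15 will receive intervention". Sections 5 (Enrollment) and 8 describe the same sequence.
- **Comparison.** Section 6.2 asks whether the groups differ in dilator progress, in FSDS and FSFI scores (the latter printed there as FISI), and in ability to have or enjoy penetrative intercourse.
- **Study duration.** The synopsis in Section 4 gives "Up to 48 months". Section 5 (Enrollment) says "We expect this to take place over approximately 24-48 months". Section 11.1 gives 24 to 48 months as the time to recruit 30 participants.
- **End of study.** Section 9: "End of study duration will be at follow up questionnaire (at 6-24 months post initial appointment and questionnaire". No calendar closing date is stated.
- **Treatment period.** Section 5.4: "The treatment period duration is 6-12 months". Section 8 (Group 2) says: "This will take place over 6-24 months in a joint psychosexual clinic".

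**The concern.** Each secondary outcome is asked once after baseline. Dilator therapy is described as progressive, and sexual function and distress can also change with time, so an answer at 6 months and one at 24 months need not mean the same thing. If calls in one group come systematically earlier, the group comparison becomes partly a comparison of elapsed time.

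Sequential enrolment gives a reason to expect that. Any calendar limit on the study shortens the follow-up available to the later group first, and the later group is always the vibrator group. With one measurement per woman and 10 to 15 women per group, later adjustment could not credibly separate group from time.

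The primary acceptability answers are affected less, through varying length of exposure and recall. Section 11.2 plans no formal test, so what is at stake is the descriptive comparison and the planning of the later efficacy studies that Section 5.3 has in view.

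**Working it through.** **1. Does the stated study duration reproduce?** Total duration = recruitment time + follow-up time. Inputs: recruitment 24 to 48 months (Section 11.1), follow-up 6 to 24 months (Section 8), stated total 48 months (Section 4).

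- 24 + 24 = 48: fits.
- 42 + 6 = 48: fits, but only with calls at the 6-month minimum for the last enrolled.
- 48 + 6 = 54 and 48 + 24 = 72: exceed the stated total by 6 to 24 months.

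So 48 months covers the full window only if recruitment ends by month 24, and covers the minimum follow-up only if it ends by month 42.

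**2. How far apart may the groups be?** The window alone allows group means to differ by up to 24 − 6 = 18 months, a ratio of 24/6 = 4. This is the bound, not an expectation.

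**3. What could a calendar limit do?** Assumptions that are not in the protocol: entry time t is even over 0 to R months, the first 15 are standard and the next 15 vibrator, and the study closes hard at month 48. Longest available follow-up = min(24, 48 − t). Standard-group women enter by month R/2, which is at most 24, so their figure is always 24.0. For the vibrator group:

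- R = 24: all enter by month 24, giving 24.0.
- R = 36: entry 18 to 36; (6×24 + 12×18)/18 = 20.0.
- R = 42: entry 21 to 42; (3×24 + 18×15)/21 = 16.3.
- R = 48: entry 24 to 48; mean 12.0, and 6/24 = 25% (about 4 of 15) cannot reach month 6.

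These are ceilings. If calls also fell evenly between month 6 and the ceiling, mean call time = (6 + mean ceiling)/2:

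| Recruitment (months) | Mean ceiling, standard vs vibrator | Mean call time, standard vs vibrator |
|---|---|---|
| 24 | 24.0 vs 24.0 | 15.0 vs 15.0 |
| 36 | 24.0 vs 20.0 | 15.0 vs 13.0 |
| 42 | 24.0 vs 16.3 | 15.0 vs 11.1 |
| 48 | 24.0 vs 12.0 | 15.0 vs 10.5* |

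*Among those able to reach month 6, whose mean ceiling is (6 + 24)/2 = 15, so (6 + 15)/2 = 10.5. This row breaks the protocol's own 6-month minimum for the others. It shows that 48 months of recruitment and a 48-month close are incompatible; it is not a compliant scenario.

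**4. Sensitivity to group size.** Section 9 also allows 10 then 15, so the vibrator group enters from 0.4R to R:

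- R = 36: (9.6×24 + 12×18)/21.6 = 20.7.
- R = 42: (7.2×24 + 18×15)/25.2 = 17.6.
- R = 48: (4.8×24 + 24×12)/28.8 = 14.0, with 6/28.8 = 21% (about 3 of 15) below 6 months.

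The standard group stays at 24.0 throughout.

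**5. Treatment period beside follow-up.** Taking the 6 to 12 months of Section 5.4 from the initial consultation, a call at 6 months could fall during treatment, and a call at 24 months would come 24 − 12 = 12 to 24 − 6 = 18 months after it ended. The protocol does not say how this period relates to the 6 to 24 months in Sections 7, 8 and 9.

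**The case against.** The window is the same for both groups and has a 6-month minimum, and nothing says that either group will be called early or late. The 48 months may be a planning figure. Section 9 ends the study at the follow-up questionnaire, and without a hard close the forced difference is zero. The worst row above is not protocol-compliant; within compliant recruitment (up to 42 months) the illustrative gap in mean call time is 0 to 3.9 months. The protocol gives no rate of change over time for any outcome, so the bias itself cannot be sized. The 24 to 48 months in Section 5 could mean the whole study, which would agree with the synopsis. A treatment period and a follow-up window can be different quantities. Finally, the comparison is secondary, descriptive and already non-randomised, so a common call month would not make it unconfounded.

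Most of this stands, and it limits the claim to a permitted imbalance of uncertain size and direction. It does not remove the point. A shared window 18 months wide is a weak safeguard, Section 11.1 does read 24 to 48 months as recruitment time, and the missing target time stands on either reading of Section 5. Other sources of confounding are no reason to leave in one that can be removed at almost no cost. Nor can an analysis plan supply the remedy later, because the protocol itself fixes when the calls are made.

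**Conclusion.** The concern holds and should be fixed. What is certain from the text is one post-baseline research contact, a window of 6 to 24 months without a target, and a vibrator group that always comes second. Following the plan as written can therefore confound the Section 6.2 comparisons with time since baseline.

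The size is conditional on even accrual, a hard close at month 48 and calls spread evenly over the available time. On those assumptions mean call time is equal for 24-month recruitment, 2.0 months shorter in the vibrator group for 36-month recruitment (15.0 vs 13.0), and 3.9 months shorter for 42-month recruitment (15.0 vs 11.1). Without a hard close nothing is forced, but the wide window remains.

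On durations, the stated 48 months is incompatible with recruitment beyond 42 months if Section 11.1 is read as recruitment time. The 6 to 12 month treatment period is not shown to contradict the 6 to 24 month statements, but the passages must be reconciled. This review does not say which is right.

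**What to change.** - Set one common target follow-up time for both groups, inside the existing 6 to 24 month window, with a tolerance chosen by the sponsor.
- Keep calls made outside the tolerance and flag them as late. Record the actual interval from initial consultation to call and report it by group.
- Restate study duration as recruitment plus that follow-up, or state the last enrolment month. If 48 months is kept, the last enrolment month for a target of T months is 48 − T: month 42 for T = 6, month 36 for T = 12 and month 24 for T = 24.
- Reconcile the durations in Section 4, Section 5 (Enrollment), and Sections 5.4, 7, 8, 9 and 11.1, and say how the treatment period relates to the follow-up window.

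The cost is a wording amendment, with no added contact. The downsides are that some calls will be flagged as late, and that a later target means either an earlier last enrolment or a longer stated study.

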Paterson et al found that women who masturbated to orgasm in private found that this appeared to maintain pleasurable genital sensitivity, but increase in pain sensitivity with higher vulvar pain sensitivity when orgasm occurs. Enhancing stimulation pleasurableness, psychological sexual arousal can mitigate normative increases in pain sensitivity during sex(Paterson, 2013).

Whipple et al investigated the effectiveness of genital self-stimulation in elevating pain thresholds. This was a study of only 10 women who applied pleasurable sensations to the anterior vaginal wall, the posterior vaginal wall, and the clitoris. Increases in pain thresholds but not tactile thresholds were noted in this group compared to distraction control (Whipple, 1988).

Use of devices in self-directed therapy for vaginismus and vulvodynia:

One study assessed the acceptability of vulvar vibration therapy as a treatment for vulvodynia. 69 patients enrolled of whom 49 were eligible for analysis. Vulvar pain and dyspareunia were the primary complaints, and median duration of these was two years and three years respectively (Zolnoun, 2008). Although this may be a somewhat different population; (the primary presenting complaint was vulvodynia or dyspareunia, as opposed to vaginismus, and only two of the 49 had ever used vaginal dilators). Furthermore, it was acknowledged in the study that the generalisability of results was limited as the study population was primarily white, married, well-educated and from a single geographical location. 83% of those surveyed who had used vulvar vibration therapy for at least two weeks had found it an acceptable and 73% found it a convenient treatment. In this study, Zolnoun et al. proposed that VVT therapeutic rationale was based on the anti-nociceptive properties of vibration and on the favourable response of vulvodynia to physical therapy.

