Genital vibration devices were found to result in improvements in sexual function, satisfaction, sexually related distress and genital sensation in women with arousal and orgasm disorders in one study enrolling 70 women, 37 of whom were followed up after a period of 3 months (Guess, 2017). This was a single-arm study enrolling women with arousal and/or orgasm disorders, so again a slightly different study population to the proposed study. Mean age was 35.5, and 66% had never or seldom used genital vibratory device. The Female Sexual Function Index (FSFI) and the Female Sexual Distress Scale (FSDS) were carried out at baseline and follow up which was at 3 months.

Herbenick et al acknowledged that vibrators are frequently recommended by clinicians for female sexual dysfunction, although there is little awareness of the correlation of this to sexual function. 2, 056 women participated in the internet based

survey (54% of the 3,800 nationally representative sample who were invited). This assessed the prevalence of vibrator use, and the relationship between vibrator use and psychological well-being. The Female Sexual Function Index was used. Prevalence of vibrator use was 52.5%, and use was significantly correlated ($P<0.001$) with having performed genital self-examination in the past month. Vibrator use was associated with more positive sexual function (including higher levels of desire and arousal and lower levels of pain). It was rarely associated with side effects (Herbenick, 2009).

Rubin et al and Billips et al published clinical guides for role of mechanical devices in treating female sexual dysfunction. These acknowledge the paucity of clinical evidence of effectiveness but also highlight the fact that these are generally safe and without significant adverse effect. (Rubin 2019; Billips 2002)

Proposed study

The acceptability of vulvar vibration therapy has been evaluated in women with vulvodynia, and found to be acceptable, however has not been assessed in women with a primary complaint of vaginismus.

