6.3 Primary endpoint

Baseline and follow up questionnaires will be used – to assess acceptability and perceived acceptability of control therapy and intervention.

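### Acceptability after vibrator use is observed only in women who stay enrolled and take one late phone call, and no reason is collected from those who leave, so the primary result is at risk of being overstated

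*Protocol*

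**What the plan says.** Protocol section 6.1 makes acceptability the primary objective. Section 6.3 gives the endpoint in one sentence: "Baseline and follow up questionnaires will be used – to assess acceptability and perceived acceptability of control therapy and intervention". It sets no denominator, percentage or threshold.

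The visit table in section 9 has two contacts. Baseline questionnaires are completed at the first; the second is a phone interview. On its timing, section 8 says: "The follow up questionnaires will be filled out by phone contact 6-24 months after the initial consultation". The same sentence limits the call to women who consent, "at the patients consent if they agree to remain enrolled in the trial for both group 1 and group 2".

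Between the two contacts, section 7 states: "although no contact in the interim will be required as part of the research project". On leavers, section 9 has one rule: "if patients withdraw consent for being enrolled in the study then follow up will discontinue". No text provides for a reason for withdrawal to be recorded, or says how withdrawal or non-response bears on acceptability. Sections 4 and 11 mark statistics as not applicable, and section 11.2 plans thematic analysis with some numerical summary of the formal questionnaires.

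No retention figure is given for this trial. Section 5 describes two earlier device studies. For the vulvodynia vibration study: "69 patients enrolled of whom 49 were eligible for analysis". For the study of a genital vibration device, which enrolled 70 women: "37 of whom were followed up after a period of 3 months".

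**The concern.** For most endpoints a dropout is a missing value. For acceptability it may be the answer: a woman who disliked the vibrator has a reason not to continue. Here such a woman could leave, or fail to answer the call, and contribute nothing on acceptability after use.

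Some such loss is plausible on the protocol's own account. Section 10 notes that patients can find these discussions embarrassing, and section 8 describes the call as an interview of about 30 minutes carried out by a doctor. It also comes late: 6 to 24 months is two to eight times the 3-month follow-up of the cited device study.

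The result has consequences. Section 5.3 treats a finding of acceptability as the step towards efficacy studies, and section 22 foresees the results supporting a recommendation of the therapy. A favourable percentage among the women who could be interviewed might be used for both without the number lost being visible.

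**Working it through.** **1. Is there a planned figure to reproduce?** No. The protocol gives no expected acceptability, threshold or dropout allowance. The check is therefore of how far the result could move under loss to follow-up.

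**2. Inputs**
- Women given a vibrator, N = 15 (section 5, Enrollment). This is an assumption, because section 8 gives 10-15 and section 11.1 gives 15-20 per arm.
- Fraction interviewed: not stated. Two ratios from section 5 serve only as an illustrative range: 37/70 = 52.9% and 49/69 = 71.0%. The second is the share eligible for analysis. The protocol does not say that the other 20 women dropped out, so it is not a retention rate in the strict sense.
- Favourable share among those interviewed: about 83%, borrowed from the vulvodynia study (section 5). That figure is itself limited to women who had used the therapy for at least two weeks.

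**3. Bounds.** With n interviewed and x favourable:
- completer figure = x/n
- worst case (all missing not accepting) = x/N
- best case (all missing accepting) = (x + N − n)/N
- width of the range = (N − n)/N, which is the fraction missing

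For N = 15:
- 0.529 × 15 = 7.9, so n = 8; 0.83 × 8 = 6.6, so x = 7
- 0.710 × 15 = 10.7, so n = 11; 0.83 × 11 = 9.1, so x = 9

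| Interviewed | Favourable | Completer figure | Worst case | Best case |
|---|---|---|---|---|
| 8 of 15 | 7 | 7/8 = 88% | 7/15 = 47% | 14/15 = 93% |
| 11 of 15 | 9 | 9/11 = 82% | 9/15 = 60% | 13/15 = 87% |

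With all 15 interviewed the three figures coincide.

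**4. Other arm sizes in the protocol.** The same steps give:
- N = 10: 4/5 = 80% (bounds 40% to 90%) and 6/7 = 86% (bounds 60% to 90%)
- N = 20: 9/11 = 82% (bounds 45% to 90%) and 12/14 = 86% (bounds 60% to 90%)

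The picture does not depend on which arm size is right.

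**5. Direction.** Let p be true acceptability, and let a and u be the retention of acceptors and non-acceptors. The completer figure is then expected to be pa / [pa + (1 − p)u]. With p = 0.60 (assumed):

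| a | u | Calculation | Completer figure |
|---|---|---|---|
| 0.8 | 0.8 | 0.48 / (0.48 + 0.32) | 60% (no bias) |
| 0.8 | 0.6 | 0.48 / (0.48 + 0.24) | 67% |
| 0.8 | 0.4 | 0.48 / (0.48 + 0.16) | 75% |
| 0.8 | 0.2 | 0.48 / (0.48 + 0.08) | 86% |
| 0.6 | 0.8 | 0.36 / (0.36 + 0.32) | 53% (understated) |

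Overstatement arises when non-acceptors are lost more often than acceptors. Equal loss gives none, and greater loss of acceptors reverses the sign.

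**The case against.** The quoted passages are ordinary consent conditions: a woman may leave, and then she is not followed. Withdrawal of study consent is the only listed ground for discontinuation. A woman who dislikes, stops or never uses the vibrator stays in the study and can say so at the call. With no interim research contact, she need not withdraw in order to stop. The endpoint also names the baseline questionnaire, which leavers will have completed. Choice of denominator and handling of missing answers commonly belong in a statistical analysis plan, and an all-supplied denominator is not excluded, since the number of vibrators given out will be known.

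Most of this stands, and it limits the point. A reader might infer that women who reject the device fall out of the denominator and that acceptability therefore is overstated. The protocol does not support that: it fixes no denominator, and nothing shows that non-acceptors will be lost more often. A reader might also take the cited ratios as forecasts of retention. One concerns eligibility for analysis, and the other comes from women with arousal or orgasm disorders, whom the protocol itself describes as a slightly different population. Nor is the completer percentage an upper bound, since the best case exceeds it in both rows of the first table.

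Two things remain. Baseline answers precede home use, so they can show only anticipated acceptability. And a later analysis plan can choose a denominator but cannot recover a reason for leaving that was never asked. That is a gap in data collection, which the protocol governs.

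**Conclusion.** The point holds as a risk to the primary result and as a cheap improvement. It is not a demonstrated bias. Acceptability after use rests on one late call to women still enrolled, and the protocol makes no provision to learn why others left.

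If between 8 and 11 of 15 women were interviewed, a completer figure of 82% to 88% would be compatible with true values from 47% to 93% (8 interviewed) or from 60% to 87% (11 interviewed), before any sampling uncertainty. These ranges rest on an assumed arm of 15, an assumed favourable share of about 83% among those interviewed, and interview fractions borrowed from other populations. If nearly all women are reached, the problem largely disappears.

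**What to change.** **Section 6.3.** State that acceptability after use will be reported over all women given a vibrator. Show the number without follow-up, the percentage among those interviewed, and the worst-case and best-case bounds. Name non-use, stopping the vibrator and withdrawal as acceptability outcomes in their own right. Withdrawal can be counted for every woman; non-use and stopping will be known only for those who answer, so the number missing should stand beside them.

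Counting every missing woman as not accepting should be one bound, not the sole primary definition. Over 6 to 24 months women may be unreachable for unrelated reasons, and that rule alone would tend to understate acceptability.

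**Section 9, criteria for discontinuation.** Offer a withdrawing woman one optional question on whether the vibrator was a reason. It must be voluntary, so that the right to leave without explanation is unaffected. It will not reach women who simply do not answer the call, which is why the bounds are still needed.

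**Cost.** A few sentences of protocol text and one optional tick-box. The stated range will be wider and less favourable than a completer percentage alone.
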